8.2.9 Exploratory Analysis

Exploratory endpoints in this clinical trial are

- Plasma biomarkers
- · PK analysis.

Plasma Biomarkers

Potential biomarkers to be measured in plasma are A β 42/40 ratio, pTau181, pTau217, NFL, GFAP and TDP43.

PK analysis

Plasma concentration-time data for buntanetap will be listed and summarized descriptively (number of subjects (N), mean, geometric mean, median, SD, coefficients of variation (CV), minimum, and maximum) for the SAF.

Plasma buntanetap PK parameters will be calculated using a non-compartmental method. Calculations will be based on the actual sampling times recorded during the study. The following PK parameters will minimally be determined, as data permit: Area under the curve (AUC), C_{max} , T_{max} , $t_{1/2}$, and CL. A separate PK SAP will include details on PK parameters derivations and statistical analyses based on the PK set.

8.2.10 Exposure to Treatment

Duration of exposure will be summarized quantitatively using the number of days on study drug for each patient, displayed by treatment group. Duration will be calculated as (last dose date – first dose date + 1).

Compliance with treatment will be assessed as the percentage of tablets taken in relation to number of tablets expected to be taken.

Compliance with study drug (%) =
$$\frac{Total\ number\ of\ tablets\ taken}{Number\ of\ tablets\ expected}$$

Exposure and compliance will be presented using summary statistics by treatment group and the pooled buntanetap-treatment group.

8.2.11 Medical History and Concomitant Medications

Medical history will be coded using the most recent version of the Medical Dictionary for Regulatory Activities (MedDRA). Additionally, a listing of the relevant medical history will be provided.

Prior and concomitant medications will be summarized by treatment group and by the pooled buntanetap-treatment group, by the number and percentage of subjects taking each medication, classified using World Health Organization (WHO) Drug Dictionary Anatomical Therapeutic Chemical (ATC) classes and preferred terms (PT).

8.2.11.1 Prohibited concomitant medication

Investigational agents are prohibited 4 weeks or five half-lives, whichever is greater, prior to entry and for the duration of the trial.

Aducanumab/Aduhelm and Lecanemab/Leqembi are prohibited for 4 weeks or five half-lives, whichever is greater, prior to entry and for the duration of the trial.

Initiation of prohibited medications during the course of the study is discouraged, however, if an excluded medication is initiated after screening, the site should consult with the Medical Monitor for further guidance.

Buntanetap is mainly metabolized by CYP3A4 in vitro. Therefore, we recommend avoiding concomitant use of strong or moderate CYP3A4 inhibitor/inducers, examples see below according to Food and Drug Administration (FDA) guidance on drug development and drug interactions.

ANVS-22002

Version 2.0, 27 February 2024

CYP3A4 inhibitors	Itraconazole, Ketoconazole, Azamulin, Troleandomycin, Verapamil
CYP3A4 inducers	Rifampicin

8.2.11.2 Permitted concomitant medication

Use of the following medications is allowed only if the participants have been stabilized for at least 4 weeks before screening and will continue to be stable throughout the study:

- tricyclic antidepressants
- antipsychotics prescribed for any reason. However, the dosage must not exceed the following for these medications: Quetiapine ≤50 mg/day, risperidone ≤1.5 mg/day, olanzapine ≤5 mg/day, and aripiprazole ≤10 mg/day

If the participant is on other antipsychotics besides the ones mentioned above, please consult the Medical Monitor before screening the participant.

psychostimulants

Discontinuation and/or change of any of the above medication during the course of the study is discouraged, however, if necessary, the site should consult with the Medical Director and Sponsor for further guidance.

For concomitant treatment with anti-cholinesterase, it is allowed to use for at least 4 weeks prior to screening.

For any anticonvulsant medications used for epilepsy or mood stabilization, neuropathic pain indications, dosing must be stable for at least 4 weeks prior to screening.

For mood-stabilizing psychotropic agents, including but not limited to lithium, dosing must be stable for at least 4 weeks prior to Screening.

Use of short acting benzodiazepines and hypnotics for treatment on an as-needed basis for insomnia or daily dosing as anxiolytics is permitted but should be avoided for 8 hours before administration of cognitive tests. For sedating medication given for any short-term use, all cognitive assessments must be administered at least 24 hours after administration of the sedative.

At this time, there is no controlled clinical data available for anyone receiving SARS-COVID19 vaccination while being treated with buntanetap. Based on the intended mechanism of actions and currently available data for these vaccine candidates and for buntanetap, it is not believed that there are specific risks to consider in participants participating in this study who have received SARS-COVID19 vaccination or who are planning to receive the vaccination. As such, SARS-COVID19 vaccination is not prohibited. If appropriate, SARS-COVID19 vaccination should be considered as a concomitant medication.

8.2.11.3 Coding and imputation of incomplete dates

All concomitant medications/therapies will be classified according to ATC level 2 group text and WHO Drug Dictionary PT. The medications will be classified into categories Prior and Concomitant drug administration based on start date and end date in relation to IMP exposure.

- Prior medications are those for which end dates of the medication/therapy are strictly before date of first administration of study drug.
- Concomitant medications are those for which the period between their start dates and end dates coincide with exposure to study drug and can be further classified into:
 - Concomitant medications starting prior to first exposure to study drug having start dates strictly before first exposure to study drug and end dates on same date or after date of first administration to study drug or are ongoing.
 - Concomitant medications starting on the date of first administration of study drug or after but before or on the date of last administration of study drug

ANVS-22002

For medication and therapies with partial dates:

- If start date is completely missing, it will be assumed that the medication started before date of first administration of study drug.
- If end date is completely missing and ongoing is not ticked, it will be assumed that the medication ended before date of first administration of study drug.
- If only the year is available, month 6 will be imputed for the purpose of classification.
- For medications/therapies where only year and month (including imputed dates) are available
 this information will be used in analogy with how complete dates are used for classification,
 e.g.:

Start date	End date	Ongoing	IMP start date	IMP end date	Classification
2020-07	2020-07		2020-08-14	2020-09-13	Prior
2020-07		No	2020-08-14	2020-09-13	Prior
2020-07		Yes	2020-08-14	2020-09-13	CM before
2020-07	2020-08		2020-08-14	2020-09-13	CM before
2020-08	2020-08		2020-08-14	2020-09-13	CM before
2020-08		No or Yes	2020-08-14	2020-09-13	CM before
2020-08	2020-09		2020-08-14	2020-09-13	CM before
2020-09	2020-09		2020-08-14	2020-09-13	CM after
2020-09		No or Yes	2020-08-14	2020-09-13	CM after

CM: Concomitant Medication

A relative day will not be calculated for medications with incomplete dates.

The concomitant medications will be presented in a summary table broken down on timing in relation to study drug (i.e., Prior and Concomitant). Each subject will only be counted once for each medication and timing category, on a PT level in each period.

One list for each timing period will be presented for the SAF. In addition, a list of anti-parkinsonian medications will be provided.

8.3 Safety Assessment

All safety summary analyses will be performed using the actual treatment for the Safety Analysis by each treatment group and by the pooled buntanetap-treatment group.

8.3.1 Adverse Events

Adverse events include but are not limited to:

- worsening or change in nature, severity, or frequency of conditions or symptoms present at the start of the study;
- subject deterioration due to primary illness;
- intercurrent illness;
- drug interaction.

An abnormal laboratory value will only be reported as an AE if the investigator considers it clinically significant, or if it leads to the participant being withdrawn from the study.

Symptoms and conditions present at the beginning of the study will be characterized, so that AEs can be defined as any new symptom, or any increase in frequency or severity of an existing symptom.

AEs will be coded according to the most recent version of the MedDRA system and will be tabulated by system organ class (SOC) and PT.

A TEAE is an undesirable event that is not present prior to medical treatment, or an already present event that worsens either in intensity or frequency following the treatment. Only TEAEs will be included in summary tables and non-TEAEs will be listed separately.

Relationship to clinical study treatment will be mapped according to the scheme below:

- Potentially related: will include all adverse events with a relationship rating of "definitely", "probably" or "possibly".
- Unlikely/not related: will include all adverse events with a relationship rating of "unlikely" or "unrelated".

An overall summary table will give

- · number of events
- number of unique events
- · number of subjects with at least one event

for:

- Overall summary of TEAEs
- Serious TEAEs
- Serious TEAE related to study drug
- TEAEs related to study drug
- TEAEs by maximum severity
- TEAEs leading to treatment discontinuation and/or Interruption of study drug
- TEAEs leading to withdrawal from study
- · TEAEs leading to death

The total number and percentage of subjects with at least one TEAE and the total number of TEAEs will be presented by SOC and PT. If more than one TEAE occurs with the same PT for the same subject, then the subject will be counted only once for that PT using the most severe and most related occurrence for the summary.

Frequent TEAEs are defined as any PT with ≥5% incidence in any of the treatment arms, which will be summarized by PT.

An AE listing by subject will display all events, and will include the verbatim term in addition to the MedDRA SOC and PT. This listing will also include all relevant eCRF data associated with the event: date of onset, date resolved, date of last dose, severity, frequency, outcome and relationship to study drug and action taken with study drug. Separate listings will be presented for subjects with treatment-emergent serious AEs (SAEs), related TEAEs, TEAEs leading to drug withdrawn, fatal TEAEs (if any).

If AE start date is incomplete, AEs with start month same as month of first administration of study drug will be regarded as TEAEs.

Adverse events will be reported to Data Safety Monitoring Board (DSMB) (see Section 8.11) per DSMB Charter.

8.3.2 Vital Signs

Descriptive summaries (mean, SD, median, minimum, and maximum) of actual values and changes from baseline for all visits at which they were assessed will be calculated for systolic blood pressure, diastolic blood pressure, pulse, respiratory rate, and oral temperature.

Shift tables showing the number of subjects who shifted from normal, abnormal not clinically significant or abnormal clinically significant at baseline to normal, abnormal not clinically significant or abnormal clinically significant at each post-baseline time of assessment will be presented.

8.3.3 Clinical Laboratory Measurements

For continuous laboratory parameters, descriptive statistics will be presented for each visit and for the changes from baseline to each subsequent visit by treatment group, and the pooled buntanetap-treatment group.

	CLINICAL SAFETY LAB TESTS	
METABOLIC PANEL	COMPLETE BLOOD COUNT	URINALYSIS
Sodium (Na)	White Blood Cell Count (WBC)	Color
Potassium (K)	Red Blood Cell Count (RBC)	Appearance
Chloride (CI)	Hemoglobin (Hb)	Specific Gravity
Carbon Dioxide (CO2)	Hematocrit (HCT)	pH
Blood Urea Nitrogen (BUN)	Mean Corpuscular Volume (MCV)	Blood
Glucose	Mean Corpuscular Hemoglobin (MCH)	Glucose
Calcium (Ca)	Mean Corpuscular Hemoglobin	Protein
Creatinine (Crn)	Concentration (MCHC)	Ketones
Bilirubin (direct and total)	Red Blood Cell Distribution Width (RDW)	Leukocyte
Albumin	Mean Platelet Volume (MPV)	Esterase
Protein Total	Platelet Count (PLT)	Nitrite
Glutamic-Oxaloacetic		Urobilinogen
Transferase (AST, SGOT)	Screening Only	Bilirubin (total)
Glutamic-PyruvateTransferase (ALT,	Hemoglobin A1C (HbA1c)	
SGPT)	Tromographi (Tro (Tro)	
Alkaline Phosphatase (ALP)		
eGFR (estimated Glomerular		
Filtration Rate)		

Additionally, clinical laboratory parameters will be categorized as low, normal, or high according to laboratory range specifications and the number and percentage of subjects in each category will be presented in shift tables.

Shift tables showing the number of subjects who shifted from normal, abnormal not clinically significant or abnormal clinically significant at baseline to normal, abnormal not clinically significant or abnormal clinically significant at each post-baseline time of assessment will be presented.

Laboratory values that are outside the normal range will also be flagged in the data listings, along with corresponding normal ranges.

If laboratory values are below the limit of quantification, the value corresponding to the limit of quantification will be used when summarizing data (e.g., if the result is <x.x, then the value x.x will be used in the statistical analysis).

8.3.4 Physical Examination

Number and percentage of normal, abnormal but not clinically significant or abnormal and clinically significant findings will be tabulated by visit for the body systems:

- skin,
- head
- eyes,
- ears,
- nose,
- throat,
- · pulmonary,
- cardiovascular,
- abdomen,
- musculoskeletal,
- extremities.

Shift tables showing the number of subjects who shifted from normal, abnormal not clinically significant or abnormal clinically significant at baseline to normal, abnormal not clinically significant or abnormal clinically significant at each post-baseline time of assessment will be presented.

Physical examination data will also be presented in listings.

Neurological Examination 8.3.5

Number and percentage of normal, abnormal but not clinically significant or abnormal and clinically significant findings will be tabulated by visit for the body systems

- cranial nerves.
- strength,
- coordination,
- reflexes.
- sensation,
- tremor,
- gait,
- mental status.

Shift tables showing the number of subjects who shifted from normal, abnormal not clinically significant or abnormal clinically significant at baseline to normal, abnormal not clinically significant or abnormal clinically significant at each post-baseline time of assessment will be presented.

Neurological examination data will also be presented in listings.

8.3.6 **Cardiac Assessments**

A 12-lead ECG will be performed prior to the administration of study drug at the timepoints of assessments.

The Investigator will enter a signed and dated clinical interpretation of the ECG trace in the eCRF. At each timepoint, absolute values and change from Baseline of ECG numeric variables will be summarised through descriptive statistics by each treatment group, and the pooled buntanetaptreatment group. Observed QTc will also be categorized into the following categories (msec) and the number and percentage of subjects in each category will be summarized at each timepoint and the overall post-baseline maximum:

- Observed: <=450, 451-480, 481-500, and >500; >450; >480
- Change from Baseline: <=10, 11-30, 31-60, and >60; >30

For ECG interpretations, the number of available observations and the number of normal, abnormal clinically significant and abnormal not clinically significant values (absolute and in percentage) will be summarized at each timepoint. The overall post-baseline worst interpretation will also be summarized.

Shift tables showing the number of subjects who shifted from normal, abnormal not clinically significant or abnormal clinically significant at baseline to normal, abnormal not clinically significant or abnormal clinically significant at each post-baseline time of assessment will be presented.

Columbia Suicide Severity Rating Scale (C-SSRS)

The number and percentage of subjects with suicidal ideation or suicidal behavior based on the C-SSRS will be summarized by treatment group and the pooled buntanetap-treatment group. Suicidal ideation or behavior are defined as:

- Suicidal ideation: A "yes" answer at any time during treatment to any one of the five suicidal ideation questions (Categories 1-5)
- Suicidal behavior: A "yes" answer at any time during treatment to any one of the five suicidal behavior questions (Categories 6-10)
- Suicidal ideation or behavior: A "yes" answer at any time during treatment to any one of the ten suicidal ideation and behavior questions (Categories 1-10)

The intensity of most severe suicidal ideation during the participant's lifetime, during the double-blind treatment period, and during the safety follow-up period will also be presented by treatment group and the pooled buntanetap-treatment group for the SAF. Intensity of most severe ideation is a sum of the 5 intensity items (Frequency, Duration, Controllability, Deterrents, and Reasons for Ideation).

Actual lethality and potential lethality on most lethal attempt will also be summarized by treatment group and the pooled buntanetap-treatment group.

Supportive listings will be provided and will include the participant number, study center number, lifetime history, and post-baseline values. Intensity of suicidal ideation, suicidal behavior type, and lethality of suicidal behavior will also be included in these listings.

A listing of all AEs occurring in participants who have suicidal ideation or suicidal behavior will also be provided.

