# 3.2. Summary of Clinical Findings

Three Phase 1 studies and two Phase 2a study have been conducted with buntanetap. For the three Phase 1 studies, the first was a single ascending dose (SAD) study in healthy volunteers; the second was a multiple ascending dose (MAD) study in healthy volunteers, and the third one was a pharmacokinetic (PK)/pharmacodynamic study of CSF in mild cognitively impaired participants (Protocol QR12001). One Phase1/2 study (Discover) was to test the safety,

Confidential Page 18 of 57

tolerability, PK and PD of buntanetap in subjects with early Alzheimer's disease (Protocol QR12005). The other Phase 2a study was a double study for both early AD and early PD participants to test buntanetap's safety, pharmacokinetics, biomarkers, and efficacy (Protocol ANVS-12003).

In the SAD trial, buntanetap was administered orally in doses of 10, 20, 40, 80, and 160 mg. Limiting side effects observed following the 160 mg dose resulted in curtailment of the study without administration of the 320 mg dose. The 160 mg dose was associated with an increased incidence of nausea and vomiting (four participants were nauseous and three vomited). Adverse events were either mild or moderate; none were severe. Buntanetap 80 mg was determined as the no observed adverse effect level.

Following oral administration, peak concentration was achieved rapidly, with mean observed  $T_{max}$  between 1.3 and 1.6 hours for both males and females at all doses.  $C_{max}$  increased with increasing dose, as did the various measures of AUC. Differences in mean observed  $C_{max}$  and AUC between males and females at each dose appeared to be related to body weight rather than gender differences.

In the MAD trial, buntanetap was administered orally in doses of 20, 40, and 60 mg 4 times a day (QID). The first two treatments were dosed for 7 days, and the third, for 10 days. Single doses were given on the first and last day to determine the pharmacokinetics of the drug. In general, the drug was well tolerated, resulting in no serious or severe adverse events and only one premature discontinuation, a participant in the 60 mg group discharged because of nausea, vomiting, dizziness and "feeling warm." The incidence of adverse events, all either mild or moderate severity, also occurred with similar frequency in the placebo group. The most common AEs were dizziness, headache, and nausea/vomiting.

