Buntanetap was absorbed rapidly after oral administration, achieving maximum plasma and CSF concentration ( $C_{max}$ ) within 1.2-1.5 hours. For the 40 and 60 mg doses, with fully defined plasma profiles, the mean terminal  $t_{1/2}$ 's were  $3.80\pm0.88$  and  $5.23\pm1.24$  hours, respectively after a single dose and  $3.53\pm1.03$  and  $4.104\pm0.91$  hours, respectively, after repeat dosing. The half-life ( $t_{1/2}$ ) of the plasma concentrations at the lower doses could not be calculated accurately. The  $C_{max}$  increased with dose (24, 144, and 2310 ng.h/mL after a single dose of 20, 40, and 60 mg, respectively and 110, 134, and 2101 ng.h/mL after multiple doses of 20, 40, and 60 mg, respectively).

In the proof of mechanism of action study (Protocol QR12001), the PK of buntanetap was measured after 10 days of administration (4x60 mg) over 12 hours in CSF and plasma of the MCI participants. The pharmacodynamics of a number of biomarkers was compared for 12 hours before the first dose at day 0 and after the last dose at day 11 of buntanetap administration. We found that the plasma concentrations of buntanetap overlapped with the plasma concentrations found in the MAD study. In this study, the N1-metabolite reached about 10 to 15%, while the level of the N8-metabolite reached about 20 to 25% of the buntanetap levels measured in plasma.

Confidential Page 19 of 57

Because a substantial proportion of the adverse events observed in AD participants treated with cholinesterase inhibitors appear to reflect the cholinomimetic properties of molecules in this class, buntanetap's highest tolerated dose is determined by the levels of the N1-metabolite in blood and brain.

While the  $t_{1/2}$  of buntanetap in plasma was 4-5 hours as seen in the SAD and MAD studies, the  $t_{1/2}$  in CSF/brain was longer than 12 hours. The concentrations of buntanetap in the brain, extrapolated from blood and CSF, were 8 times higher than in plasma. 10 days of treatment with buntanetap normalized CSF levels of sAPP $\alpha$  and  $\beta$ , tau,  $\alpha$ SYN and a series of inflammatory markers. The concentration and persistence of buntanetap in the brain suggests that much lower doses of drug administered once daily could achieve the desired pharmacological effect.

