#### 9.4.1 End of Trial Visit

This constitutes the participants' last clinical visit during the study. The end of trial visit will consist of the following: admission procedures, blood sampling, all psychometric and safety tests, and discharge procedures. Fasting is required for safety laboratory tests.

Participants should arrive fasted in the morning after an overnight fast. Clinical safety labs will be drawn and sent to the central lab for analysis.

After safety lab, participants will be provided a low-fat light meal before completing functional and cognitive evaluations, a physical and neurological exam, collecting vital signs, ECG, and reviewing and recording adverse events and concurrent medications. Sites should take detailed notes of the contents of all meals provided to the participants.

If no medical or compliance concerns are identified, the participant will move on to the PK sampling phase, which will entail the following procedures:

- 1) Collect initial samples of blood 10ml (hour 0) with venipuncture unless PI deems inappropriate.
- 2) Administer last dose of assigned study drug after the hour 0 sampling.
- 3) Collect blood (10mL) at the 1hr, 2hrs and 4hrs timepoints. Blood should be taken within  $\pm$  10 mins of times.
- 4) Perform the final safety monitoring.

Prior to discharge from the clinic, vital signs should be recorded, and a review of AE(s) and concomitant medications should be conducted. Upon determination by the Investigator (or qualified designee) that the participant is stable, the participant will be discharged. If a participant experiences an unstable AE, please contact the Medical Monitor for guidance on the appropriate course of action to be taken.

Confidential Page 42 of 57

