# **APPENDIX 1: SCHEDULE OF EVENTS**

Study Period	Screening/Baseline  Day -42 to 0		At-Home Treatment		Unscheduled Visit k	Early Discontinuation Visit
Visit Timing			6 weeks ± 7 days	12 weeks ± 7 days (end-of-trial) b		
Procedure	Screening j (up to 42 days before Day 0)	Baseline (Day 0)	Clinic Visit -	Clinic Visit	Clinic Visit	Clinic Visit
Informed consent	X					
Inclusion and exclusion criteria	X	X				
Demography information	X					
Full physical and neurological examination	X	X	X	X	X	X
Height, Weight, BMI	X					
Medical and psychiatric history (includes substance use)	X					
Urine pregnancy test (WOCBP only)	X	X	X	X	X	X
MMSE 	X	X		X		X
ADCS-CGIC		X d	Xe	Xe		Xe
ADAS-Cog11		X	X	X		X
ADCS-ADL		X	X	X		X
DSST		X	X	X		X
C-SSRS	X	X	X	X	X	X
Safety laboratory tests c	X	X	X	X	X	X
12-lead ECG	X	X	X	X		X
Vital signs a	X	X	X	X	X	X

Confidential Page **56** of **57** 

Protocol ANVS-22002 Ver. 3.1; 09-25-2023

Study Period	Screening/Baseline  Day -42 to 0		At-Home Treatment		Unscheduled Visit k	Early Discontinuation Visit
Visit Timing			6 weeks ± 7 days 12 weeks ± 7 days (end-of-trial) b			
Procedure	Screening j (up to 42 days before Day 0)	Baseline (Day 0)	Clinic Visit	Clinic Visit	Clinic Visit	Clinic Visit
Randomization		X				
Genetic sample (ApoE)		X				
Study intervention		X g	$X^h$	$X^{I}$		
Study intervention compliance review			X	X		
AE/SAE review	X	X	X	X	X	X
Concomitant medication review	X	X	X	X	X	X
PK sampling		X		X		
Sampling for blood biomarkers		X		X		
24-hour phone follow-up		X	X	X	X	X

<sup>a Vital sign will include sitting blood pressure, pulse, temperature, respiration rate.

Confidential Page 57 of 57

<sup>b Participants that drop out before the initial 9 weeks of study treatment will complete the Early Discontinuation visit and participants that drop out after the initial 9 weeks of study treatment will complete the End-of-Trial visit.

<sup>c Safety labs should be taken fasted.

<sup>d ADCS-CGIC evaluation only.

<sup>e ADCS-CGIC evaluation and scoring the scale.

g Participants are given one pill during the visit after taking pre-dose (0h) blood samples and the pills for the remaining 6 weeks at the end of the visit.

<sup>h Participants are given pills for the remaining 6 weeks at the end of the visit.

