The objective of this study is to assess efficacy and safety of buntanetap in participants with mild to moderate AD. We only tested 80 mg once daily (QD) in Phase 2a study in AD participants. During the dose-finding Phase 2a PD study, a dose-response curve between 0 and 80 mg QD was observed with 10 and 20 mg QD showing the best benefit. Therefore, we want to do a similar dose-ranging trial to test the efficacy of 7.5 mg, 15 mg and 30 mg QD buntanetap.

4 Study Objectives and Endpoints

Objective Endpoint

Primary

The primary objective is to assess efficacy and safety of buntanetap in participants with mild to moderate AD.

1. Alzheimer's Disease Assessment Scale-Cognitive Subscale 11 (ADAS-Cog 11)

Change in ADAS-Cog 11 from Baseline to Week 12.

ADAS-Cog 11 is an 11-item score measuring cognitive functions and non-cognitive functions such as mood and behavior. Total scores range from 0-70, with higher scores indicating greater cognitive impairment.

2. Alzheimer's Disease Cooperative Study-Clinical Global Impression of Change (ADCS-CGIC)

ADCS-CGIC is a validated categorical measure of change in the participant's clinical condition between baseline and follow-up visits. It measures whether the effects of active treatment are substantial enough to be detected by a skilled and experienced clinician on the basis of a clinical interview and examination. It relies on both direct examination of the participant and an interview of the study partner. A skilled and experienced clinician who is blinded to treatment assignment rates the participant on a 7-point Likert scale, ranging from 1 (marked improvement) to 7 (marked worsening). Lower scores indicate better improvement.

3. Safety and tolerability

- Adverse events (AE)
- Severity of AEs
- Drug related AEs
- · AEs leading to study discontinuation
- Electrocardiogram (ECG) findings
- Clinical laboratory test results
- Vital sign measurements
- Physical examination findings

Objective

ANVS-22002

Endpoint

Secondary

Assess improvement on AD participants' daily living and cognitive functions

Alzheimer's Disease Cooperative Study-Instrumental Activities of Daily Living Scale (ADCS-ADL)

The ADCS-ADL is a 23-item inventory developed as a rater-administered questionnaire answered by the participant's study partner. The ADCS-ADL measures both basic and instrumental activities (instrumental activity items 6a, 7-23) of daily living by participants with a lower score indicating greater severity.

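### The Week 12 ECG precedes the dose and none is scheduled near peak, so the QTc tables cannot describe peak exposure; at Week 6 the protocol does not fix the time since dose

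*SAP*

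**What the plan says.** SAP section 4 lists "Electrocardiogram (ECG) findings" among eight safety and tolerability items under the primary objective. SAP 8.3.6 then sets the timing: "A 12-lead ECG will be performed prior to the administration of study drug at the timepoints of assessments". It plans QTc categories (up to above 500 ms, and change up to above 60 ms) at each timepoint and for the overall maximum after baseline.

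Protocol 9.4.1 gives the Week 12 order. After fasting labs and a light meal come the cognitive tests and examinations, with "collecting vital signs, ECG, and reviewing and recording adverse events and concurrent medications". The PK phase follows: hour 0 blood, then "Administer last dose of assigned study drug after the hour 0 sampling", then blood at 1, 2 and 4 h and a closing safety check whose content is not defined. The last step names no ECG: "Prior to discharge from the clinic, vital signs should be recorded, and a review of AE(s) and concomitant medications should be conducted". Baseline (Protocol 9.2) has the same order.

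Week 6 differs. Protocol 9.3 includes an ECG but no in-clinic dose. Footnote h of the Schedule of Events says only: "Participants are given pills for the remaining 6 weeks at the end of the visit". Neither place says whether that morning's home capsule is held. Under Protocol 7.2 the capsule is taken once daily in the morning, just before food.

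**The concern.** The drug peaks early and leaves plasma quickly. Protocol 3.2 reports mean Tmax "between 1.3 and 1.6 hours for both males and females at all doses" and, for half-life, a value that "of buntanetap in plasma was 4-5 hours as seen in the SAD and MAD studies". An ECG a full dosing interval after the last capsule therefore sees little parent drug in plasma, while participants are on site for blood sampling at 1–2 h with no ECG scheduled then.

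The stake is how the output will be read. Nothing labels the QTc tables as pre-dose, so the overall post-baseline maximum would pass for the worst QTc on drug. A QTc effect tied to peak concentration could be missed, and the clean table taken as evidence against it. The protocol treats QTc as relevant: exclusion criterion 4 sets QTcF limits.

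Week 6 adds a second problem. If some participants take the home capsule before the visit and others do not, one table would combine trough and near-peak readings. The documents name no time-since-dose record with which to separate them.

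**Working it through.** The plan states no figure for residual drug at the ECG, so there is none to reproduce. The check uses the documents' own PK.

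**Inputs**
- Dosing interval: 24 h (Protocol 7.2, once daily in the morning).
- Tmax: 1.3–1.6 h in the single-dose study and 1–2 h in Phase 2a (Protocol 3.2). I use 1.5 h and vary it from 1 to 2 h.
- Plasma half-life (Protocol 3.2): 4–5 h as the summary figure. Individual means run from 2.76 h (80 mg, Phase 2a) to 5.23 h (60 mg single dose, SD 1.24). At 5 and 10 mg it could not be calculated accurately.

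**Residual at the Week 12 ECG**

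Method A assumes a mono-exponential fall from peak: fraction = 2^(−(24 − Tmax)/t½). With Tmax 1.5 h:
- t½ 4 h: 2^(−22.5/4) = 2^(−5.625) = 2.03%
- t½ 5 h: 2^(−22.5/5) = 2^(−4.5) = 4.42%
- t½ 2.76 h: 2^(−22.5/2.76) = 2^(−8.15) = 0.35%

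Method B is a one-compartment oral curve at steady state, with the absorption rate solved from Tmax.

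| t½ (h) | Method A | Method B |
|---|---|---|
| 2.76 | 0.35% | 0.43% |
| 4 | 2.03% | 2.25% |
| 5 | 4.42% | 4.76% |
| 5.23 | 5.07% | 5.43% |
| 6.47 (5.23 + 1.24) | 8.98% | 9.42% |

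With Tmax from 1 to 2 h, the mean half-lives give 0.31% (2.76 h, Tmax 1 h, Method A) to 6.02% (5.23 h, Tmax 2 h, Method B). At 6.47 h the highest value is 10.2%.

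**Week 6 if the home capsule was taken first**

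For an ECG h hours after the capsule, fraction = 2^(−(h − 1.5)/t½).
- h = 2: 91.7% (t½ 4 h) or 93.3% (5 h)
- h = 4: 64.8% (4 h) or 70.7% (5 h)

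A Week 6 reading could thus be at about 65%–93% of peak, or at about 2%–5% if the capsule was held. The documents do not settle which.

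**Post-dose vital signs at Week 12**

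These follow the 4 h sample, and Protocol 4.2 adds at least 1 h of observation. At 4–5 h after the dose the same formula gives:
- t½ 4 h: 64.8% to 54.5%
- t½ 5 h: 70.7% to 61.6%
- t½ 2.76 h: 53.4% to 41.5%

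**CSF and brain**

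Protocol 3.2 puts this half-life above 12 h, so at least 2^(−24/12) = 25% remains after 24 h. The low percentages above apply to plasma only.

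**The case against.** The best defence is that the plan never promised an assessment at peak. The objective is general safety, ECG is one of eight descriptive items, and Protocol 6.11 plans no formal safety comparisons. Protocol 3.1 reports a negative hERG assay and no adverse QT effect, under non-clinical findings. Protocol 4.3 argues that the existing safety data make the present measures sufficient. The top dose, 30 mg once daily, is well below the 160 mg single doses and 60 mg four times daily given before. This lowers the urgency, and it stands. It does not make a pre-dose maximum informative about peak.

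Three stronger readings are tempting, and the documents do not support them:
- A reader might infer that every post-baseline ECG is at trough. Only Week 12 is secure. Week 6 rests on the SAP sentence. SAP section 3 makes the SAP prevail over the protocol, but an analysis plan does not instruct sites. The early discontinuation ECG has no fixed interval from the last capsule.
- A reader might infer that the trial cannot meet a stated ECG objective. No peak-exposure or concentration-QTc aim is stated, and 12 weeks of pre-dose ECGs against placebo can show sustained or cumulative change.
- A reader might infer that a heart-rate effect would go unseen. Vital signs, which include pulse, are recorded before discharge, when roughly 42%–71% of peak remains. Nor does the dizziness and fainting in Protocol 5.1 point to an ECG signal: that section reports these effects on placebo too.

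The percentages are also extrapolated from 40–80 mg to 7.5–30 mg. They cover parent drug only. No half-life is given for the N1 metabolite, whose levels Protocol 3.2 says determine the highest tolerated dose.

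**Conclusion.** The point holds in a limited form. The Week 12 ECG is pre-dose by both documents, with parent plasma drug at about 2%–5% of peak, 0.3%–6% across the mean half-lives given, and about 10% at the longest mean plus one SD. No ECG is scheduled near Tmax after an in-clinic dose. The QTc tables and the post-baseline maximum therefore cannot describe QTc effects at peak exposure, but remain usable for sustained changes against placebo. At Week 6 the time since dose is not established, so readings of different kinds may be pooled.

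This assumes 24 h between capsules, a roughly mono-exponential decline, and half-lives at the trial doses similar to those at 40–80 mg. The conclusion tolerates considerable error in these: even 10% of peak is not peak exposure. It is a gap in coverage and labelling that is cheap to close, not a failure of the safety objective.

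**What to change.** - At Week 12, take the already scheduled ECG at the 1 h or 2 h PK sample instead of before the dose. Keep the pre-dose baseline ECG as reference.
- Record the time since last dose for every ECG, including Week 6 and early discontinuation.
- Amend SAP 8.3.6 to tabulate Week 12 QTc change as post-dose, against placebo, and to state which readings enter the post-baseline maximum.
- Reconcile SAP 8.3.6 with Protocol 9.3 and the Schedule of Events, so that it is clear whether the Week 6 ECG is before or after that day's capsule.

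The cost is a protocol amendment with IRB approval (Protocol 22.2), one extra data field, and the loss of the Week 12 trough ECG. No procedure is added, and participants already stay through the 4 h sample. The concurrent placebo arm deals with time-of-day and meal effects.

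SAP 8.9 records that the interim re-estimation was already done when the SAP was written, so the change may come too late. If Week 12 visits are complete, label the ECG tables and the post-baseline maximum as planned pre-dose readings that do not cover peak exposure, and state that the Week 6 time since dose was not fixed by the protocol.
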